1.4 Exploratory Objectives

- To determine the effect of the combination on vasculopathy, immune infiltration, and tumor necrosis by staining pathologic specimens for VEGF/VEGFR expression, phosphoTie-2 and other targets.
- To investigate immune responses in the periphery to VEGFR, Tie-2, and other angiogenic molecules and tumor-specific antigens as a function of treatment.

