3.1 Eligibility Criteria

In order to be eligible for participation in this trial, the participant must meet the following criteria on screening examination:

- 3.1.1** Be willing and able to provide written informed consent for the trial.
- 3.1.2** Be ≥ 18 years of age on day of signing informed consent.
- 3.1.3** Have measurable disease based on RECIST 1.1.
- 3.1.4** In dose escalation (Phase I), patients must have histologically or cytologically confirmed metastatic disease from any solid tumor that is incurable and fulfills one of the following criteria:
 - a) Has demonstrated progression of disease following at least one line of effective systemic therapy. Prior treatment with anti-CTLA-4 antibody (including ipilimumab) is allowable
 - OR
 - b) For which effective therapy does not exist
- 3.1.5** In dose expansion (part 2), patients must have histologically or cytologically confirmed unresectable or metastatic melanoma, renal cell carcinoma, ovarian cancer, or colorectal cancer.
- 3.1.6** Renal cell patients must have had at least one prior VEGF TKI.
- 3.1.7** Ovarian cancer patients must be resistant to platinum therapy (i.e. within 6 months of last platinum therapy).
- 3.1.8** Patients with colorectal cancer should have progressed on at least one fluorouracil plus irinotecan or oxaliplatin containing regimen.
- 3.1.9** Patients with melanoma should have unresectable or metastatic disease. Melanoma patients with BRAF V600E or V600K mutation-positive melanoma who have previously received a BRAF inhibitor with or without a MEK inhibitor) are eligible.
- 3.1.10** In the dose expansion cohort patients should be willing to provide tissue from a newly obtained core or excisional biopsy of a tumor lesion (pre-treatment) and an on-treatment biopsy. Newly-obtained is defined as a specimen obtained up to 6 weeks (42 days) prior to initiation of treatment on Day 1. Patients for whom newly-obtained samples cannot be provided (e.g., inaccessible, participant safety concern, or unwilling to undergo biopsy) may submit an archived specimen only upon agreement from the Sponsor. An on-treatment biopsy will be collected approximately halfway through the induction period, about 6 weeks from the start of study treatment (sometime between Cycle 2 Day 8– Cycle 3 Day 1).
- 3.1.11** Have a performance status of 0 or 1 on the ECOG Performance Scale (see Appendix A) up to 28 days before treatment initiation

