3.2 Exclusion Criteria

The participant must be excluded from participating in the trial if the participant:

- 3.2.1** Is currently participating and receiving study therapy or has participated in a study of an investigational agent and received study therapy or used an investigational device within 4 weeks of the first dose of treatment.
- 3.2.2** Has a diagnosis of immunodeficiency including participants infected with Human Immunodeficiency Virus (HIV).
- 3.2.3** Is receiving systemic steroid therapy or any other form of immunosuppressive therapy within 7 days prior to the first dose of trial treatment.
- 3.2.4** Has a known history of active TB (Bacillus Tuberculosis).
- 3.2.5** Has had a prior anti-cancer monoclonal antibody (mAb) within 4 weeks prior to study Day 1 or who has not recovered (i.e., \leq Grade 1 or at baseline) from adverse events due to agents administered more than 4 weeks earlier.
- 3.2.6** Has had prior chemotherapy, targeted small molecule therapy, or radiation therapy within 2 weeks prior to study Day 1 or who has not recovered (i.e., \leq Grade 1 or at baseline) from adverse events due to a previously administered agent.

Note: Participants with \leq Grade 2 neuropathy are an exception to this criterion and may qualify for the study.

Note: If participant received major surgery, they must have recovered adequately from the toxicity and/or complications from the intervention prior to starting therapy.

- 3.2.7** Has a known additional malignancy that is progressing or requires active treatment. Exceptions include basal cell carcinoma of the skin or squamous cell carcinoma of the skin that has undergone potentially curative therapy or in situ cervical cancer.
- 3.2.8** Lesions suspected to be at higher-risk for bleeding such as bowel involvement with tumor that invades into the bowel wall or involves the intraluminal component of bowel by imaging or direct visualization or central pulmonary lesions.
- 3.2.9** Ulcerated skin lesions
- 3.2.10** Poorly-controlled hypertension as defined BP $> 150/100$ mmHg, or SBP > 180 mmHg when DBP < 90 mmHg, on at least 2 repeated determinations on separate days within 3 months prior to study enrollment.
- 3.2.11** History within 6 months prior to treatment of myocardial infarction, severe/unstable angina pectoris, CABG, NYHA class III or IV CHF, stroke or TIA.

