- 3.2.21** Has a history or current evidence of any condition, therapy, or laboratory abnormality that might confound the results of the trial, interfere with the participant's participation for the full duration of the trial, or is not in the best interest of the participant to participate, in the opinion of the treating investigator.
- 3.2.22** Has known psychiatric or substance abuse disorders that would interfere with cooperation with the requirements of the trial.
- 3.2.23** Is pregnant or breastfeeding, or expecting to conceive or father children within the projected duration of the trial, starting with the pre-screening or screening visit through 120 days after the last dose of trial treatment.

- 3.2.24** Patient with ovarian cancer and colorectal cancer who have received prior therapy with an anti-PD-1, anti-PD-L1, or anti-PD-L2 antibody. Melanoma and renal cell carcinoma patients who received prior anti-PD-1 or anti-PD-L1 or CTLA-4 antibodies are allowed to participate.
- 3.2.25** Has received trebananib or another angiopoietin-2 directed therapy (prior treatment with bevacizumab is not an exclusion criteria)
- 3.2.26** Has active Hepatitis B (e.g., HBsAg reactive) or Hepatitis C (e.g., HCV RNA [qualitative] is detected).
- 3.2.27** Has received a live vaccine or live-attenuated vaccine within 30 days prior to the first dose of study drug. Administration of killed vaccines is allowed.

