^F Biopsy of site(s) of pre-existing disease will be performed up to 6 weeks (42 days) prior to initiation of treatment on Day 1. On-treatment biopsies should be performed approximately midway through the Induction period, approximately 6 weeks from the start of study treatment (sometime between Cycle 2 Day 8 – Cycle 3 Day 1). If for any reason removal of tissue requires a greater procedure, the biopsy must be done >28 days from the last planned dose trebananib

^G Serial blood/serum samples to be collected prior to the administration of pembrolizumab at the following time points: Cycle 1 Days 1, 8, and 15; Prior to Day 1 of every odd cycle (Cycle 3, Cycle 5, Cycle 7, etc.); End of treatment visit.

^H Tumor markers: CEA to be done on participants with colorectal cancer on day 1 of every cycle. CA125 to be done on participants with ovarian cancer on day 1 of every cycle.

^I If trebananib is discontinued due to an AE, participants may omit any Day 8 and Day 15 visits/assessments going forward.

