12. TUMOR TISSUE COLLECTION AND CORRELATIVE STUDIES BLOOD SAMPLING

Correlative sciences will include fresh biopsies of pre-existing sites of disease and following treatment to assess histologically for vasculopathy, immune infiltration, and tumor necrosis; stain pathologic specimens for VEGF/VEGFR expression, phosphoTie2; monitor circulating levels of and development of anti-trebananib antibodies as a function of treatment. Baseline and on-treatment values of a number of inflammatory and angiogenic cytokines will be monitored. Pilot studies will include the investigation of immune responses to other angiogenic molecules as a function of treatment. Flow cytometry of PBMC will be monitored for changes in levels of naïve and memory CD4, CD8 and other lymphocyte populations. Cellular and humoral immune responses to established antigens as a function of treatment will be performed. These will include melanosomal differentiation antigens as well as novel tumor associated antigen targets, Muc-1, CEA, CA-125, and NY-Eso-1 as examples.

12.1 Fresh tumor biopsies:

Biopsies of fresh tumor will be obtained prior to treatment initiation on day 1 and approximately halfway through the induction period (between cycle 2 day 8 and cycle 3 day 1). Dedicated funds are currently available at our institution for obtaining post-treatment biopsies in patients receiving immune based therapies.

Formalin fixed-paraffin embedded (FFPE) tumor slices will be prepared and H&E stained for assessment of TIL in pre- and post-treatment tumor samples. To identify different immune cell populations (effector/memory/ CD8 cells, T regulatory cells, dendritic cells, tumor associated macrophages, NK cells, TEM) immunohistochemical staining will be performed on FFPE tumor slices using the following antibodies:

CD3, CD4, CD8, CD25, FoxP3, Indoleamine 2,3 deoxygenase-1 (IDO), CD11c, CD83, CD86, CD56, CD14, CD16, PD-L1, and Tie-2.

We have recently developed immunohistochemical staining on paraffin embedded tissues for PD-L1, PD-L2, TIM-3 and LAG-3 through our Center for Immuno-oncology Pathology Core [REDACTED] PD-L1 IHC has recently been established in a CLIA approved laboratory and we are working to finalize the remaining assays for CLIA laboratory conduct. We may also send tissue out to an outside laboratory for PD-L1 testing.

[REDACTED]

[REDACTED]

[REDACTED]

[REDACTED]

1. Chen BJ et al., Clin Cancer Res. 2013 Jul 1;19(13):3462-73, PMID:23674495

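### The 42-day window for the pre-treatment biopsy is longer than the washouts, so a qualifying baseline can precede further prior therapy and partly confound the exploratory paired tissue change

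*Combined protocol and SAP*

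**What the plan says.** **Biopsy timing.** Eligibility criterion 3.1.10 fixes how old a fresh specimen may be: "Newly-obtained is defined as a specimen obtained up to 6 weeks (42 days) prior to initiation of treatment on Day 1". Footnote F of the Study Calendar (Section 9) repeats the limit: "Biopsy of site(s) of pre-existing disease will be performed up to 6 weeks (42 days) prior to initiation of treatment on Day 1". Section 12.1 gives no lower bound: "Biopsies of fresh tumor will be obtained prior to treatment initiation on day 1". The second biopsy falls about six weeks into treatment, between Cycle 2 Day 8 and Cycle 3 Day 1.

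**Washouts.** Exclusion 3.2.6 reads "Has had prior chemotherapy, targeted small molecule therapy, or radiation therapy within 2 weeks prior to study Day 1", and 3.2.5 reads "Has had a prior anti-cancer monoclonal antibody (mAb) within 4 weeks prior to study Day 1". Exclusion 3.2.25, on angiopoietin-2 agents, notes that "prior treatment with bevacizumab is not an exclusion criteria", so for bevacizumab only the four-week antibody limit applies.

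**Archived tissue.** Under 3.1.10, patients who cannot give a fresh specimen "may submit an archived specimen only upon agreement from the Sponsor".

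**Use of the tissue.** The first exploratory objective (1.4) is "To determine the effect of the combination on vasculopathy, immune infiltration, and tumor necrosis", assessed by staining tumor specimens. Section 14.8 asks for 20 paired biopsies. It proposes as an endpoint the proportion of patients whose CD137 M2 macrophages fall by half or more, tested against a null of 0.20. Archival tissue is named there only for relating baseline expression to response. The study summary states that there is no control.

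**The concern.** A paired tissue change can be read as an effect of the combination only if nothing else that acts on the tissue happens between the two samples. Here a patient can be biopsied, go on receiving another anticancer treatment, complete the washout and start study drugs, and the earlier specimen still qualifies as the baseline.

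By the protocol's own account, some of that other treatment acts on what is being measured. Section 2.1.3 says that VEGF inhibits dendritic-cell maturation and that blocking it helps T cells cross endothelium. It also reports more immune infiltrate with ipilimumab plus bevacizumab than with ipilimumab alone. Section 2.3.1 suggests that VEGF blockade normalizes tumor vessels. It describes anti-angiogenic antibody or fusion-protein treatment as standard in colorectal cancer and bevacizumab as active in ovarian cancer. Renal patients must have had a VEGF TKI (3.1.6), which as a small molecule carries only the 14-day washout. Colorectal patients are 37 of the 53 planned for expansion (14.1, 14.2).

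At stake is the interpretation of the paired biopsies, which patients undergo for this comparison.

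**Working it through.** **Step 1. Overlap of the windows.** Days on which a permitted biopsy can precede permitted prior therapy = biopsy window − washout.

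- Chemotherapy, small molecules, radiation: 42 − 14 = 28 days (day −42 to day −14).
- Anti-cancer antibodies: 42 − 28 = 14 days (day −42 to day −28).

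The calendar's screening column runs from day −28 to day −1, but 3.1.10 and footnote F give the biopsy its own limit. Even if 28 days applied, 28 − 14 = 14 days would remain for chemotherapy and 28 − 28 = 0 for antibodies.

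**Step 2. Is the gap closed elsewhere?** Sections 3.1.10, 12.1, 12.3 and 14.8 and footnote F set no order between the biopsy and the last prior dose. The recovery clauses in 3.2.5 and 3.2.6 concern adverse events, not tissue. Section 14.8 makes no allowance for intervening therapy.

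**Step 3. Reproduce the plan's power.** Inputs from 14.8: n = 20, null 0.20, alternative 0.47, exact binomial, two-sided 0.10, stated power at least 80%. With equal tails the test rejects at 0 or at 8 or more.

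- Size: P(X ≥ 8 | 20, 0.20) = 0.032. Adding P(X = 0) = 0.80^20 = 0.012 gives 0.044.
- Power: P(X ≥ 8 | 20, 0.47) = 0.802.

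The stated figure reproduces. If the two-sided region is instead built from the least likely outcomes, rejection is at 0 or at 7 or more, with size 0.098 and power 0.904, which also agrees. I use 8 or more below.

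**Step 4. Illustration of the possible effect.** The share f and rate q are my assumptions; neither is in the documents. Each pair has chance f of intervening therapy, and in such a pair the endpoint is met with probability q whatever the study drugs do. The overall rate is then p = (1 − f) × (rate in clean pairs) + f × q.

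| Scenario | f | q | p | P(X ≥ 8 of 20) |
|---|---|---|---|---|
| No drug effect (clean rate 0.20) | 0 | – | 0.20 | 0.032 |
| Intervening therapy mimics an effect | 0.10 | 0.30 | 0.21 | 0.042 |
| | 0.25 | 0.40 | 0.25 | 0.102 |
| | 0.50 | 0.50 | 0.35 | 0.399 |
| True effect (clean rate 0.47) | 0 | – | 0.47 | 0.802 |
| Intervening therapy masks the effect | 0.10 | 0.20 | 0.443 | 0.727 |
| | 0.25 | 0.20 | 0.4025 | 0.593 |
| | 0.50 | 0.20 | 0.335 | 0.344 |

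The bias can run either way, and it is small if few pairs are affected.

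**Step 5. Cost of restricting the set.** For m pairs, take the smallest r with P(X ≥ r | m, 0.20) ≤ 0.05.

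| m | r | Upper-tail size | Power at 0.47 |
|---|---|---|---|
| 20 | 8 | 0.032 | 0.802 |
| 18 | 8 | 0.016 | 0.673 |
| 15 | 7 | 0.018 | 0.609 |
| 10 | 5 | 0.033 | 0.547 |

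The set sizes are examples, not estimates of how many pairs would remain.

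**The case against.** The strongest reply is that the worst case is contrived. Consent must precede protocol procedures (10.4.1), colorectal patients should already have progressed on a qualifying regimen (3.1.8), and adverse events must have recovered. A day −42 specimen followed by four more weeks of chemotherapy therefore needs either an early study biopsy followed by other treatment, or reuse of a routine-care specimen. This stands as an argument that the case may be uncommon. It does not close the gap: progression on one regimen does not rule out a later one, and 10.4.1 accepts routine-care results obtained before consent within the time frame.

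Second, little rests on these data. The tissue work is exploratory, and the documents do not link prior anti-VEGF treatment or chemotherapy to CD137 M2 macrophages, the only tissue endpoint with a power statement. That stands and limits the weight of the point.

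Third, ordering the biopsy after the last dose does not remove the tissue's recovery from that dose. A specimen taken the next day satisfies the rule, and withdrawal effects still unfold before week 6. That stands too: the rule removes intervening dosing only.

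Fourth, dropping affected pairs costs power (Step 5). Patients have also already been treated under the present wording (12 colorectal and 4 renal in expansion), so a new rule gives two baseline definitions. This is a good reason not to make exclusion mandatory.

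**Conclusion.** The point holds as a gap in specimen timing. The plan accepts as baseline a fresh biopsy that precedes up to 28 days of chemotherapy, small-molecule or radiation treatment, or up to 14 days of antibody treatment. For those pairs, the change attributed to the combination is partly confounded in an uncontrolled comparison. The lengths follow directly from the stated windows. The frequency and direction are not given, so the figures in Step 4 depend on assumed inputs.

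Three stronger readings are tempting and not supported:

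- A reader might infer that a large share of the 20 pairs is affected. The windows show what is permitted, not what occurs, and no document gives a share.
- A reader might infer that affected pairs say nothing about the combination. They still span the start of study treatment, so they are confounded in part rather than uninformative.
- A reader might infer that archived tissue serves as the paired baseline. Section 3.1.10 lets it replace a fresh specimen, but 14.8 names it only for baseline-expression analyses. The paired set needs a clarifying sentence, not a correction.

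The primary safety objectives (1.2) and the disease-control test in colorectal cancer (14.2) are unaffected.

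**What to change.** 1. For patients still to be enrolled, state in 3.1.10, footnote F and 12.1 that the fresh pre-treatment biopsy is taken after the last dose of prior anticancer therapy and within the existing 42 days. Washouts do not change and no biopsy is added.
2. For all patients, including those already treated, record the biopsy date and the date of the last prior anticancer dose. Prior cancer treatments are already reviewed under 10.3.1.1, so existing pairs can be classified in the same way.
3. In 14.8, state that paired-change analyses use fresh pairs. Report the result for all fresh pairs, together with a sensitivity analysis limited to pairs with no intervening prior therapy.

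The cost is a timing sentence in three places, two dates in the data and an analysis-set sentence. Some routine-care specimens would no longer qualify as the paired baseline. The sensitivity set will be smaller and less powerful, as Step 5 shows, so it should be read beside the full set and not in place of it. Carry-over from recent therapy remains and should be acknowledged when the paired results are reported.

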3.1.13 Negative protein on screening urinalysis

3.1.14 Female participant of childbearing potential should have a negative serum pregnancy test performed during the screening period.

Female participants of childbearing potential (Section 5.11.2) must be willing to use an adequate method of contraception as outlined in Section 5.11.2 – Contraception, for the course of the study through 120 days after the last dose of study medication. Should a woman become pregnant or suspect she is pregnant while she is participating in this study, she should inform her treating physician immediately.

Note: Abstinence is acceptable if this is the usual lifestyle and preferred contraception for the participant.

3.1.15 Male participants of reproductive potential (Section 5.11.2) must agree to use an adequate method of contraception as outlined in Section 5.11.2- Contraception, starting with the first dose of study therapy through 120 days after the last dose of study therapy.

Note: Abstinence is acceptable if this is the usual lifestyle and preferred contraception for the participant.

3.2 Exclusion Criteria

The participant must be excluded from participating in the trial if the participant:

- 3.2.1** Is currently participating and receiving study therapy or has participated in a study of an investigational agent and received study therapy or used an investigational device within 4 weeks of the first dose of treatment.
- 3.2.2** Has a diagnosis of immunodeficiency including participants infected with Human Immunodeficiency Virus (HIV).
- 3.2.3** Is receiving systemic steroid therapy or any other form of immunosuppressive therapy within 7 days prior to the first dose of trial treatment.
- 3.2.4** Has a known history of active TB (Bacillus Tuberculosis).
- 3.2.5** Has had a prior anti-cancer monoclonal antibody (mAb) within 4 weeks prior to study Day 1 or who has not recovered (i.e., \leq Grade 1 or at baseline) from adverse events due to agents administered more than 4 weeks earlier.
- 3.2.6** Has had prior chemotherapy, targeted small molecule therapy, or radiation therapy within 2 weeks prior to study Day 1 or who has not recovered (i.e., \leq Grade 1 or at baseline) from adverse events due to a previously administered agent.

Note: Participants with \leq Grade 2 neuropathy are an exception to this criterion and may qualify for the study.

Note: If participant received major surgery, they must have recovered adequately from the toxicity and/or complications from the intervention prior to starting therapy.

- 3.2.7** Has a known additional malignancy that is progressing or requires active treatment. Exceptions include basal cell carcinoma of the skin or squamous cell carcinoma of the skin that has undergone potentially curative therapy or in situ cervical cancer.
- 3.2.8** Lesions suspected to be at higher-risk for bleeding such as bowel involvement with tumor that invades into the bowel wall or involves the intraluminal component of bowel by imaging or direct visualization or central pulmonary lesions.
- 3.2.9** Ulcerated skin lesions
- 3.2.10** Poorly-controlled hypertension as defined BP $> 150/100$ mmHg, or SBP > 180 mmHg when DBP < 90 mmHg, on at least 2 repeated determinations on separate days within 3 months prior to study enrollment.
- 3.2.11** History within 6 months prior to treatment of myocardial infarction, severe/unstable angina pectoris, CABG, NYHA class III or IV CHF, stroke or TIA.
- 3.2.12** History within 3 months prior to treatment of Grade 3-4 GI bleeding/hemorrhage, treatment resistant peptic ulcer disease, erosive esophagitis or gastritis, infectious or inflammatory bowel disease, diverticulitis, pulmonary embolus, or other uncontrolled thromboembolic event.

- 3.2.13** Patients who are less than 4 weeks post-op after major surgery.
- 3.2.14** History of allergic reactions attributed to compounds of similar chemical or biologic composition to pembrolizumab and trebananib including history of allergic reactions to bacterially produced proteins.
- 3.2.15** Has known active central nervous system (CNS) metastases and/or carcinomatous meningitis. Participants with previously treated brain metastases may participate provided they are stable (without evidence of progression by imaging for at least four weeks prior to the first dose of trial treatment and any neurologic symptoms have returned to baseline), have no evidence of new or enlarging brain metastases, and are not using steroids for at least 7 days prior to trial treatment. This exception does not include carcinomatous meningitis which is excluded regardless of clinical stability.
- 3.2.16** Has active autoimmune disease that has required systemic treatment in the past 2 years (i.e. with use of disease modifying agents, corticosteroids or immunosuppressive drugs). Replacement therapy (eg., thyroxine, insulin, or physiologic corticosteroid replacement therapy for adrenal or pituitary insufficiency, etc.) is not considered a form of systemic treatment.
- 3.2.17** Treatment within 30 days prior to enrollment/randomization with strong immune modulators including but not limited to systemic cyclosporine, tacrolimus, sirolimus, mycophenolate mofetil, methotrexate, azathioprine, rapamycin, thalidomide, and lenalidomide.
- 3.2.18** Uncontrolled intercurrent illness including, but not limited to, ongoing or active infection, interstitial lung disease or active, non-infectious pneumonitis, nephritis, pancreatitis, symptomatic congestive heart failure, unstable angina pectoris, cardiac arrhythmia, or psychiatric illness/social situations that would limit compliance with study requirements.
- 3.2.19** Has a history of (non-infectious) pneumonitis/interstitial lung disease that required steroids or current pneumonitis/interstitial lung disease..
- 3.2.20** Has an active infection requiring systemic therapy.
- 3.2.21** Has a history or current evidence of any condition, therapy, or laboratory abnormality that might confound the results of the trial, interfere with the participant's participation for the full duration of the trial, or is not in the best interest of the participant to participate, in the opinion of the treating investigator.
- 3.2.22** Has known psychiatric or substance abuse disorders that would interfere with cooperation with the requirements of the trial.
- 3.2.23** Is pregnant or breastfeeding, or expecting to conceive or father children within the projected duration of the trial, starting with the pre-screening or screening visit through 120 days after the last dose of trial treatment.

- 3.2.24** Patient with ovarian cancer and colorectal cancer who have received prior therapy with an anti-PD-1, anti-PD-L1, or anti-PD-L2 antibody. Melanoma and renal cell carcinoma patients who received prior anti-PD-1 or anti-PD-L1 or CTLA-4 antibodies are allowed to participate.
- 3.2.25** Has received trebananib or another angiopoietin-2 directed therapy (prior treatment with bevacizumab is not an exclusion criteria)
- 3.2.26** Has active Hepatitis B (e.g., HBsAg reactive) or Hepatitis C (e.g., HCV RNA [qualitative] is detected).
- 3.2.27** Has received a live vaccine or live-attenuated vaccine within 30 days prior to the first dose of study drug. Administration of killed vaccines is allowed.

